9.9. Subject card

Study subjects must be provided with the address and telephone number of the main contact for information about the clinical study.

The investigator (or designate) must therefore provide a "subject card" to each subject. In an emergency situation this card serves to inform the responsible attending physician that the subject is in a clinical study and that relevant information may be obtained by contacting the investigator.

Subjects must be instructed to keep subject cards in their possession at all times during the study duration.

205626 (S SONNEI MONO GMMA SBVGH-003 [H03_03TP])
Protocol Amendment 6 Final

9.10. Holding rule and safety monitoring

9.10.1. Holding rule

The following holding rule has been defined for the study:

• At least one subject developing a ≥ Grade 3 symptomatic neutropenia considered possibly, probably or definitely related to vaccination.

The Investigator must notify GVGH/GSK immediately if the holding rule is met and should halt any further vaccination until further notice. Vaccination can only be resumed after formal review of unblinded data by the IDMC and formal greenlight to proceed with further vaccination (please refer to the IDMC charter).

9.10.2. Safety monitoring

The SRT will monitor the safety of subjects throughout the study. The SRT will review blinded data, assess safety signals and make recommendations to the IDMC and to the Sponsor concerning continuation, termination, or other modifications of the study based on the observed adverse effects.

An IDMC will be established by GSK Biologicals for the purpose of monitoring the study and to provide independent, non-binding advice on safety and ethics. The IDMC will provide recommendations about stopping, holding, continuing or modifying the trial.

The frequency of IDMC sessions and other operational details are described in the IDMC charter. In case of a serious safety issue during the study, GSK Biologicals will inform the IDMC as well as fulfil its regulatory obligation expeditiously.

10. SUBJECT COMPLETION AND WITHDRAWAL

10.1. Subject completion

A subject who returns for the concluding visit foreseen in the protocol is considered to have completed the study.

10.2. Subject withdrawal

Withdrawals will not be replaced.

10.2.1. Subject withdrawal from the study

From an analysis perspective, a 'withdrawal' from the study refers to any subject who did not come back for the concluding visit foreseen in the protocol.

All data collected until the date of withdrawal/last contact of the subject will be used for the analysis.

205626 (S SONNEI MONO GMMA SBVGH-003 [H03_03TP]) Protocol Amendment 6 Final

A subject is considered a 'withdrawal' from the study when no study procedure has occurred, no follow-up has been performed and no further information has been collected for this subject from the date of withdrawal/last contact.

Investigators will make an attempt to contact those subjects who do not return for scheduled visits or follow-up.

Information relative to the withdrawal will be documented in the eCRF. The investigator will document whether the decision to withdraw a subject from the study was made by the subject himself/herself, or by the investigator, as well as which of the following possible reasons was responsible for withdrawal:

- Serious adverse event.
- Unsolicited non-serious adverse event.
- Solicited adverse event.
- Protocol violation (specify).
- Consent withdrawal, not due to an adverse event*.
- Moved from the study area.
- Lost to follow-up.
- Other (specify).

*In case a subject is withdrawn from the study because he/she has withdrawn consent, the investigator will document the reason for withdrawal of consent, if specified by the subject, in the eCRF.

Subjects who are withdrawn from the study because of SAEs/AEs must be clearly distinguished from subjects who are withdrawn for other reasons. Investigators will follow subjects who are withdrawn from the study as result of a SAE/AE until resolution of the event (see Section 9.5.1.2).

10.2.2. Subject withdrawal from study vaccine/placebo or challenge agent

A 'withdrawal' from the study vaccine/placebo or challenge agent refers to any subject who does not receive the complete treatment, i.e. when no further planned dose or challenge is administered from the date of withdrawal. A subject withdrawn from the study vaccine/placebo or challenge agent may not necessarily be withdrawn from the study as further study procedures or follow-up may be performed (safety or immunogenicity) if planned in the study protocol.

Information relative to premature discontinuation of the study vaccine/placebo or challenge agent will be documented on the Vaccine Administration page/screen of the eCRF. The investigator will document whether the decision to discontinue further vaccination/challenge administration was made by the subject himself/herself, or by the investigator, as well as which of the following possible reasons was responsible for withdrawal:

205626 (S SONNEI MONO GMMA SBVGH-003 [H03_03TP])
Protocol Amendment 6 Final

- Serious adverse event.
- Unsolicited non-serious adverse event.
- Solicited adverse event.
- Not willing to be vaccinated or to receive the challenge agent.
- Other (specify).

11. STATISTICAL METHODS

11.1. Primary endpoint

Efficacy

VE will be evaluated with:

• Rate of shigellosis (fulfilling the protocol primary case definition) occurring within a period starting with the challenge visit and lasting up to the end of the inpatient stay, in all subjects.

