Reiter's syndrome	A post-dysenteric reactive arthritis, with ocular and/or urethral inflammation, which has an onset typically 1 to 3 weeks after the onset of diarrhea, has been reported to occur in patients with shigellosis.	negative Shigella cultures in stools. Data suggest that the risk of reactive arthritis following shigellosis may be higher in persons carrying the human leukocyte antigen (HLA)-B27, thus the exclusion of subjects with a positive HLA-B27 test at screening.							

205626 (S SONNEI MONO GMMA SBVGH-003 [H03_03TP])
Protocol Amendment 6 Final

Important Potential/Identified Risk	Data/Rationale for Risk	Mitigation Strategy
Risk related to antibacterial therapy	Other (challenge phase) There are documented side effects with the use of antibiotics.	However, ciprofloxacin, the antibiotic given to all subjects on the 5th day after challenge, is generally well-tolerated. The most frequently reported drug related events for all indications of ciprofloxacin therapy have been nausea, diarrhea, abnormal liver function tests, vomiting, and rash which are all mild to moderate in most cases. The most common symptoms that happen after taking TMP-SMX are nausea, vomiting, loss of appetite, skin rash and itching. All subjects will be monitored closely and given adequate care when the need arises.

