- They have diarrhea (any severity stool Grade 3 or higher) and two or more of the following symptoms: severe abdominal pain/cramps, severe nausea, severe headache, severe myalgia, severe arthralgia, gross blood in ≥ 2 stools, any fever (≥ 38.0°C measured orally), or any vomiting.
- They experience unexpectedly severe events such as hypotension (disproportionate to volume loss), renal dysfunction, or altered mental state (e.g. somnolence) at the discretion of the investigators.
- A study physician determines early treatment is warranted for other reasons.

A subject receiving early antibiotic treatment will still remain on the unit until the planned day of discharge (the 9th day of inpatient stay: Day 65). On that day, if a subject is clinically well and has had at least 2 negative stool cultures, collected at least 6 hours apart, for *S. sonnei*, s/he will be discharged. A subject that, on the planned day of discharge, still had S. *sonnei* isolated from the Day 64 stools will be asked to remain in the unit until s/he is no longer shedding. A subject still shedding 48 hours after initiation of ciprofloxacin will be switched to a Septra DS (1 tablet twice a day for five days). If a subject is still positive 48 hours after the second-line antibiotic is administered, a culture and antibiotic sensitivity test will be obtained and therapy initiated based on sensitivity results. If a subject has two consecutive negative stool samples and is eligible to be discharged from the inpatient stay but did not finish his treatment course, s/he can be given the remaining doses to complete at home.

Following discharge, subjects will return at 28 days (Visit 6), 56 days (Visit 7) and 6 months (Visit 8) after challenge for outpatient clinical assessment. During these visits, clinical assessment will be done to assess their general health status and find out about the occurrence of AESI, any AE and SAE.

[figure not shown]
Subjects will be advised at the time of their discharge to contact the study staff/doctor if they feel unwell. The subjects will be followed up until 6 months after the challenge. At the last study visit, at 6 months after challenge, the subject will be reviewed for the occurrence of any AESI and the site staff will ensure all AEs are resolved.

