- Stool sample for inflammatory response before challenge at Visit 5 (Day 57) and daily, post challenge, during inpatient stay (Day 57 to Day 64).
- Stool sample: for microbiome testing at Visit 1 and Visit 5, for *S. sonnei* specific sIgA at Visit 1, Visit 2, Visit 4 and 7 days after challenge (Day 64) and stool analysis, culture and qPCR daily during inpatient stay (from Visit 5 to 7 days after challenge [Day 57 to Day 64] or prolonged until 2 consecutive negative stool samples if subject still shedding).

205626 (S SONNEI MONO GMMA SBVGH-003 [H03_03TP])
Protocol Amendment 6 Final

- Type of study: self-contained.
- **Data collection**: Standardized electronic Case Report Form (eCRF).
- **Safety monitoring:** An Independent Data Monitoring Committee (IDMC) will be established to monitor the safety of subjects throughout the study. The IDMC will review unblinded data, to assess safety signals and make recommendations to the Sponsor concerning continuation, termination, or other modifications of the study based on the observed adverse effects. The membership and roles of the IDMC will be outlined in the IDMC charter.

The safety review team (SRT) will monitor the safety of subjects throughout the study. The SRT will review blinded data, assess safety signals and make recommendations to the IDMC and Sponsor concerning continuation, termination, or other modifications of the study based on the observed adverse effects.

A dedicated Safety Management Plan will be prepared to ensure appropriate safety reporting responsibilities and roles are defined.

Refer to Section 9.10 for detailed description of holding rule and safety monitoring.

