- ⁴ Sampling to be done 7 days after challenge agent administration (i.e., Day 64).
- ⁵ Additionally, hematology is repeated weekly until resolution if neutropenia occurs. On the day of vaccination/challenge, sampling will be done before vaccination/challenge.
- ⁶ Urine dipstick to be done for all subjects and, in case of abnormal results, a urine culture is to be performed (urinalysis).
- ⁷ Before vaccination/challenge (Day 1/Day 57 sample can be collected by the subject at most a week before and stored as described in the Investigator Manual and SPM.
- ⁸ Sampling to be done daily during inpatient stay and if subject is still shedding 7 days post-challenge administration (Day 64). However, all subjects even if not shedding anymore will remain in the inpatient stay until 7 days post-challenge and will be discharged on Day 65.
- ⁹ Samples collection can be performed between Day 56 and Day 57.

205626 (S SONNEI MONO GMMA SBVGH-003 [H03_03TP]) Protocol Amendment 6 Final

Whenever possible, the investigator should arrange study visits within the interval described in Table 5.

Table 5 Intervals between study visits (Amended: 23 July 2019)

Interval	Optimal length of interval	Allowed interval
Screening visit → Visit 1	-7 days	-45 days – -1 days
Visit 1 → Phone Call	3 days	2 days - 6 days
Visit 1 → Visit 2	7 days	7 days - 10 days
Visit 1 → Visit 3	28 days	26 days - 33 days
Visit $3 \rightarrow$ Phone call	3 days	2 days - 6 days
Visit 3 → Visit 4	7 days	7 days - 10 days
Visit 3 → Visit 5	28 days	26 days - 33 days
Visit 5 → Inpatient stay	9 days	9 days - as needed
Visit 5 → Visit 5 post-challenge blood draw (Amended: 23 July 2019)	7 days (Amended: 23 July 2019)	7 days – 10 days (Amended: 23 July 2019)
Visit 5 → Visit 6	28 days	28 days - 35 days
Visit 5 → Visit 7	56 days	49 days - 63 days
Visit 5 → Visit 8	180 days	166 days - 194 days

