9.1.3.3. Solicited events after challenge phase

During the challenge phase after the subjects have received the challenge agent, events associated with the administration of the challenge agent will be collected and recorded by the investigator in the CRF. These events include diarrhea, abdominal pain, abdominal cramps, gas, anorexia, nausea, headache, myalgia, malaise, arthralgia, fever, and vomiting beginning the day of administration of study challenge agent until 7 days after challenge (i.e., Day 64). Any unresolved events will be followed to resolution or stabilization. Oral rehydration will be initiated and recorded for subjects with a Grade 2 or higher AE of diarrhea, vomiting, dysentery or dehydration. The hydration of subjects developing diarrhea will be maintained with oral electrolyte solutions by offering at least 1.5 mL for each gram of diarrheal stool lost, as tolerated. Subjects who develop vomiting will be offered at least 1.0 mL for each gram of emesis lost, as tolerated. Subjects will be evaluated by a physician who will consider intravenous hydration for subjects who:

- Cannot tolerate oral fluids,
- Experience fluids loss that exceeds their ability to drink replacement fluids,
- Have > 1000 mL deficit in intake in a 24 hour period,
- Experience weight loss of more than 5%,
- Have urine specific gravity > 1.030 for 12 hours,
- Have syncope or near-syncope,
- Grade 3 tachycardia, or
- Grade 3 hypotension.

If the subject is unable to tolerate fluids by mouth and intravenous fluids are deemed necessary by the assessing physician, a 0.9% sterile saline solution 1-liter bolus will be administered intravenously. This bolus will be repeated as needed to resolve Grade 2 and above symptoms at the discretion of assessing physician. Fluid maintenance will be continued using 0.45% NaCl, 5% dextrose, and 20 mEq KCL per liter at a rate of 100 mL/hour until subject is able to resume oral rehydration. If the subject develops grade 4 hypotension despite the aggressive fluid management, the subject will be transferred from the inpatient unit to a hospital setting.

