11.2. Secondary endpoints

Efficacy

VE, in subjects receiving the 1790GAHB vaccine vs. placebo, will be also measured during inpatient stay (Day 57 to Day 64) against:

- Rate of shigellosis *as defined by* the CHIM working group case definition for shigellosis occurring within a period starting with challenge visit and lasting until the end of the inpatient stay, in all subjects. (*Amended: 23 July 2019*)
- Rate of shigellosis, as defined by: severe diarrhea OR moderate diarrhea with fever or with one or more moderate constitutional/enteric symptom OR dysentery [[≥2 loose stools with gross blood (hemoccult positive) in 24 hours] AND [≥1 reportable constitutional/enteric symptom]].
- Rate of more severe shigellosis as defined by: severe or moderate diarrhea with fever or with one or more severe constitutional/enteric symptom OR dysentery [[≥2 loose stools with gross blood (hemoccult positive) in 24 hours] AND [*oral temperature* ≥38.0°C OR ≥1 severe constitutional/enteric symptom]]. (Amended: 23 July 2019)
- Shedding of *S. sonnei* strain 53G.
 - Shedding of *S. sonnei* strain 53G is defined as positivity of at least one stool sample either by culture or qPCR or both.
- Severe diarrhea
- More severe diarrhea.
- Dysentery.

205626 (S SONNEI MONO GMMA SBVGH-003 [H03_03TP])
Protocol Amendment 6 Final

- Weight of all grade 3-5 stools.
- Total number of all grade 3-5 stools.
- Confirmed S. sonnei 53G shedding AND moderate or severe diarrhea OR dysentery OR presence of oral temperature ≥ 38.5 °C OR presence of one or more severe intestinal symptoms (abdominal pain, cramping, nausea, vomiting, gas, anorexia).
- Disease not fulfilling the protocol primary case definition for shigellosis associated or not with mild to moderate symptoms including: passing loose stool (not meeting the protocol definition of moderate or severe diarrhea), abdominal pain, abdominal cramps, gas, anorexia, nausea, headache, myalgia, malaise, arthralgia, fever, vomiting and IV fluid administration.
- Time to onset of shigellosis after challenge, according to the protocol primary case definition.

Safety

Solicited adverse events

• Occurrence of each solicited local and systemic adverse event within 7 days after each vaccination.

Unsolicited adverse events

• Occurrence of unsolicited AEs within 28 days after vaccination and after challenge, according to Medical Dictionary for Regulatory Activities (MedDRA) classification.

Serious adverse events

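### The primary endpoint window ends at a discharge date that the protocol gives as Day 64, as Day 65, and as open-ended for subjects still shedding; one fixed end day is needed

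*Protocol*

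**What the plan says.** Section 11.1 (repeated in the synopsis) counts primary cases "occurring within a period starting with the challenge visit and lasting up to the end of the inpatient stay, in all subjects". It states no day.

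The protocol describes the end of the inpatient stay in three ways:

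- **Day 64.** Section 11.2 says that secondary efficacy "will be also measured during inpatient stay (Day 57 to Day 64) against" the listed outcomes. The study design list in Section 3.2 sets the primary completion date at the end of the inpatient stay and labels it Visit 5, Day 64. Section 11.12.1 times the first analysis, of efficacy data, after completion of Visit 5 (Day 64). Section 9.1.3.3 collects solicited post-challenge events "beginning the day of administration of study challenge agent until 7 days after challenge (i.e., Day 64".
- **Day 65.** Section 6.6.12 and footnote 8 to Table 4 run the stay to Day 65, and Section 3.2 names Day 65 as the planned discharge day.
- **Open-ended.** Under Section 3.2, a subject with *S. sonnei* "isolated from the Day 64 stools will be asked to remain in the unit until s/he is no longer shedding". Table 5 gives the allowed interval as "9 days - as needed". The sampling schedule runs stool analysis, culture and qPCR to Day 64 "or prolonged until 2 consecutive negative stool samples if subject still shedding".

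Under Section 4.3, both routes to a primary case require shedding: shedding with moderate or severe diarrhea, or shedding with an oral temperature of at least 38.5°C. Section 11.8 estimates VE as one minus a ratio of simple proportions.

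**The concern.** A subject whose Day 64 stools are negative is observed until Day 65. A subject whose stools are positive is observed for longer, with no stated maximum. The rule that lengthens the stay is persistent shedding, which is a required component of the primary outcome and is itself a listed efficacy target in Section 11.2. Taken literally, only subjects who already meet that component gain extra days in which diarrhea or fever can complete the definition. A risk ratio of simple proportions has no term for unequal observation time. If the vaccine shortens shedding, the extra days fall mainly on placebo recipients, and any case first met in those days raises the apparent VE.

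Section 11.2 has the same problem internally. Its heading fixes Day 57 to Day 64, but the bullet for the CHIM working group definition runs to the end of the inpatient stay. At stake is which cases count in the only endpoint with a success criterion, and whether that choice could be made after the data are seen.

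**Working it through.** **1. The planned figures, reproduced.** Section 11.4 assumes a true VE of 70%, one-sided alpha of 5%, a placebo attack rate of 58% and 22% non-evaluable subjects.

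- Vaccine share of cases under the alternative: (1 − 0.70)/(2 − 0.70) = 0.2308, tested against 0.5.
- With 21 cases the exact binomial test rejects at 6 or fewer vaccine cases. Exact alpha is 0.039 and power is 0.808, which matches the stated 80%.
- Evaluable subjects: 2 × 21/(0.58 × 1.30) = 55.7. Dividing by 0.78 gives 71.4, rounded up to 72, as stated.
- Per arm: 36 × 0.78 ≈ 28 evaluable, so 28 × 0.58 = 16.2 placebo cases and 16.2 × 0.30 = 4.9 vaccine cases are expected.

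None of these steps uses the length of follow-up, so fixing the window leaves all of them unchanged.

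**2. The passages side by side.** Take a subject who sheds, has Day 64 stools positive, and first meets the diarrhea or fever criterion on Day 66 while still in the unit.

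| Text followed | Primary case? |
|---|---|
| Section 11.1 with the stay prolonged under Section 3.2 and Table 5 | Yes |
| Section 11.1 with the stay ending on Day 64 (primary completion date) or Day 65 (Section 6.6.12) | No |

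On the first reading, this primary case has no onset time inside the Day 57 to Day 64 period that heads the time-to-onset endpoint.

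**3. Size at the planned result.** The protocol does not name the method for its 90% CI. Miettinen-Nurminen and log risk-ratio limits are both shown, with 28 per arm.

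| Vaccine vs placebo cases | VE | Lower limit, Miettinen-Nurminen | Lower limit, log RR |
|---|---|---|---|
| 5 vs 16 | 68.8% | +38.5% | +35.9% |
| 5 vs 17 | 70.6% | +42.7% | +40.1% |
| 9 vs 15 | 40.0% | −1.2% | −2.6% |
| 9 vs 16 | 43.8% | +6.4% | +4.8% |

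The first two rows are near the design expectation, and both succeed. The last two are at the boundary, where one placebo case reverses the conclusion.

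**4. Size across a range.** The documents give no rate of cases first met after Day 64. Assume 0, 1, 2 or 5 percentage points, all in placebo, which is the worst case. The probabilities use the log-RR 90% limits.

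| Late placebo cases | Apparent VE if no effect to Day 64: 1 − 0.58/(0.58 + late) | Chance of success if no effect to Day 64 | Apparent VE if true VE is 70%: 1 − 0.174/(0.58 + late) |
|---|---|---|---|
| 0 | 0% | 0.042 | 70.0% |
| 1 point | 1.7% | 0.049 | 70.5% |
| 2 points | 3.3% | 0.057 | 71.0% |
| 5 points | 7.9% | 0.090 | 72.4% |

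With 28 per arm, 5 points is 1.4 late cases on average.

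**The case against.** The strongest reply is that Day 64 is the intended end. The glossary defines the primary completion date as final data collection for all primary outcomes, and that date is set at Day 64. The first efficacy analysis follows Day 64. Section 11.2 says secondary efficacy is also measured from Day 57 to Day 64, which suggests the same period as the primary endpoint. This makes Day 64 the most plausible intention and the right day for the fix. It does not settle the text: Section 11.1 names no day, and Sections 3.2 and 6.6.12 and Tables 4 and 5 end the same stay later or leave it open.

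The second reply also largely stands. A late case must fail the definition through Day 64, still be culture-positive on Day 64 despite antibiotics from Day 62, and then newly develop diarrhea or fever. Section 1.3.1 expects effective antibiotics to reduce or eliminate symptoms within 24 hours. Prolonged shedders who are already cases add nothing.

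Four stronger readings are tempting, and the documents do not support them:

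- **The window inflates VE.** It can, but no count of late cases is given. If the vaccine affects neither shedding nor disease, prolongation is equal between arms in expectation.
- **Primary and secondary attack rates cover different periods.** That is one reading; the protocol may be using the two descriptions as synonyms.
- **The 9 versus 15 reversal shows a fragile trial.** Any binary criterion turns on one case at its boundary, and the planned result lies well away from it.
- **Ciprofloxacin diarrhea contaminates the late days.** Section 1.3.1 does state that "The most frequently reported drug related events for all indications of ciprofloxacin therapy have been nausea, diarrhea" are among its effects. But antibiotics are planned for both arms from Day 62, and Days 62 to 64 lie inside any window ending on Day 64.

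**Conclusion.** The point holds as a defect in the endpoint definition. The sole confirmatory endpoint has no single end day. On the literal reading, observation time depends on a component of the outcome, in a direction that can favour an effective vaccine. The heading of Section 11.2 and its CHIM bullet carry the same conflict.

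The likely numerical effect is small. Sample size, case target and power are unaffected, and at a true VE of 70% the assumed 1 to 5 points of late placebo cases add 0.5 to 2.4 points of VE. The rise in the chance of false success, from 0.042 to between 0.049 and 0.090, rests on two assumptions: late cases occur in placebo only, and the vaccine has no effect on disease up to Day 64. The practical risk is a borderline result in which one late case, and the reading chosen for it, decides success. A statistical analysis plan may fix the day, but the contradiction stands in the protocol itself.

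**What to change.** In Sections 11.1 and 11.2, and in the synopsis, define all efficacy endpoints over one fixed period for every subject: from challenge through the end of calendar Day 64, regardless of the actual discharge date. Give the end as a calendar day only. A 168-hour limit would fall part-way through Day 64 and create a second end point. Use the same wording in the CHIM bullet, so that it agrees with its heading, with the primary completion date and with Section 11.12.1. Report events during a prolonged stay separately and do not count them as endpoint cases.

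The cost is about one sentence in each section. Discharge and treatment rules are untouched, and the sample size does not change. The small downside is that a rare late-onset case is not counted. An analysis restricted to onsets before the first antibiotic dose is optional and is not needed to cure this point.
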